15.1.3 Protocol deviations

The number and percentage of patients with protocol deviations will be given in the clinical study report classified as significant and not significant deviation as defined in the data review protocol. In addition, the investigators' assessment of inclusion and exclusion criteria at screening will be presented.

15.1.4 Analysis sets

The number and percentage of patients included in the analysis sets, together with a breakdown of the reasons for the assignment to the analysis sets, will be provided in the clinical study report. A tabular listing of all patients excluded from the ITT and from the PP sample will be provided.

15.2 Demographic and other baseline characteristics

Summary tables will be provided for the ITT population by means of descriptive statistics and frequency tables and may be repeated for other populations as appropriate.

The following demographic data and baseline characteristics will be presented:

Demographics:

- Gender
- Ethnicity
- Age
- Height, weight, BMI
- Pregnancy test (female patients only)

Vital signs:

- Blood pressure
- Pulse rate

Current status of coronary heart disease:

- Duration of coronary heart disease
- Angina pectoris (stable/unstable, CCS-classification)
- Indication for PCI (single-vessel disease, multiple-vessel disease, in-stent-stenosis, revision of venous bypass stenosis, no PCI – including details)
- Stenosis severity pre-PCI

Laboratory results at screening:

- Coagulation status
- Hemogram
- Liver function profile
- Kidney function profile
- Electrolytes
- Hs-Troponin-T

For reference ranges see DMP. A listing of each abnormal laboratory value will be provided.

15.3 Previous and concomitant treatment and medications

Summary tables will be provided for the ITT population for:

Relevant medical history and current medical conditions, including indication to concomitant medication (MedDRA-coded: preferred term and organ system class).

Previous and concomitant medications (ATC-coded: anatomical main group, therapeutic subgroup, chemical substance) – separately for screening and follow-up.

Previous treatment (non-drug therapy) related to cardiac disease (surgical interventions ...) will be listed and grouped ad-hoc if applicable. Same applies for new or changed non-drug therapies recorded in follow-up.

15.4 Study treatment

Summary tables will be provided for the ITT population for:

- Duration of PCI (end minus start time)
 - all patients, separately for patients with/without PCI
- ACT measurement during PCI
 - Number of measurements
 - below / within / above target range, i.e. < 300, 300 - 450, > 450 s
 - separately for ACT measurement prior to argatroban treatment, first ACT measurement after first bolus, ...
- Extent of argatroban exposure
 - Duration of argatroban treatment
 - Number of bolus administered
 - Dosing interruptions and adaptations
 - Argatroban dose
 - separately for each bolus dose, infusion dose
 - Argatroban cumulative dose per kg (in mg/kg)
$$\left(\sum_b bolus_b (\mu\text{g/kg}) + \sum_i infusion_i (\mu\text{g/kg/min}) * duration_i (\text{min}) \right) / 1000$$
 - Argatroban cumulative dose (in mg)

In addition, a listing will be provided depicting the individual PCI duration, ACT measurements and argatroban dosing scheme per patient.

- Measured argatroban plasma concentration at follow-up
- ACT measurement at argatroban-free status (follow-up)
 - Summary statistics per center

- below / within / above normal range,
i.e. < 80, 80 – 160, > 160 s (center1), < 97, 97 – 133, > 133 s (center 2)
- listing of ACT values outside the normal range
- Diluted thrombin time (dTt) at follow-up

In addition, a listing will present the argatroban concentration and coagulation status (dTt and ACT) at follow-up together with the QT interval at ECG-3.

Additional drugs administered will be presented (ATC-coded: therapeutic subgroup, chemical substance)

15.5 Efficacy evaluation

The primary data set for the efficacy analysis will be the ITT analysis set. Additional analyses will be performed for the PP analysis set. Note that whereas trials to show superiority always use the ITT population as primary analysis, results for both ITT and PP population are of interest in non-inferiority trials. It may actually be easier to show non-inferiority in the bigger sample of the ITT population, especially in case of many protocol deviations. This underpins the importance of the PP analysis in non-inferiority trials.

Subgroup analyses will be performed as described in Section 14.6.

Summary tables will be provided by means of descriptive statistics and frequency tables, as appropriate.

15.5.1 12-lead ECG

The following will be presented at screening, during treatment and at follow-up:

- Overall interpretation (investigator and blinded ECG-reader assessment); if abnormal, clinically significant
- Measured QT interval, corrected QT interval
- Interpretation of QT interval: prolonged; if prolonged, clinically significant

Primary endpoint (see section 12.1):

- Difference in QTc interval between ECG-2 and ECG-1 ($\Delta QTc = QTc_2 - QTc_1$)
- Test of statistical hypothesis (see Section 14.3)

Secondary endpoints (see section 12.2):

- Difference in QTc interval between ECG-3 and ECG-1 ($QTc_3 - QTc_1$)

- Proportion of patients with $QTc_2 > 500$ ms
- Proportion of patients with $QTc_3 > 500$ ms
- Proportion of patients with $QTc_2 - QTc_1 > 60$ ms
- Proportion of patients with $QTc_3 - QTc_1 > 60$ ms

In addition, a listing will tabulate the individual response data, i.e. QTc_1 , QTc_2 , QTc_3 as well as gender and cumulative Argatroban dose.

The dependence of QTc interval on gender and cumulative Argatroban dose will furthermore be investigated in plots. If applicable, linear correlation of QTc interval and cumulative Argatroban dose will be assessed.

Heart rate and Measured RR interval will be presented at screening, during treatment and at follow-up.

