13.3.5.1. QTc - Statistical hypothesis (primary variable)

Following measurements of QTc will be made for each patient:

- Prior to first bolus dose of argatroban: QTc₁
- immediately after cardiac intervention in a status of full anticoagulation with argatroban: QTc₂
- > 8 but ≤ 28 hours after termination of prolonged argatroban infusion: QTc₃

The statistical hypothesis of this study refers to the difference QTc₂ minus QTc₁ = Δ QTc:

H₀: Δ QTc > 10 ms

H_A: Δ QTc ≤ 10 ms.

H_0 will be tested by a one-sided one sample t-test with a significance level of alpha=5%. Data from all patients with measurements QTc₁ and QTc₂ will be included in the analysis of Δ QTc.

Additionally, Δ QTc as well as QTc₁ and QTc₂ will be described by descriptive statistics (mean, standard deviation, median, minimum, maximum, and 95%-confidence interval). An individual patient listing will be provided with QTc₁, QTc₂, Δ QTc, QTc₃ and the difference QTc₃ minus QTc₁.

The analysis of the primary variable will be based on the ITT sample. It will be repeated for the PP sample. The study report will contain a statement about difference in study results between the ITT and PP sample.

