13.1 Definition of analysis sets

Each patient will be assigned to appropriate analysis populations for statistical analysis. The different analysis populations are:

Enrolment set (all enrolled population): The enrolment set includes all patients who were included in the study (eligibility screening conducted), even if no treatment was performed. The enrolment set is the starting point for the description of the patients' disposition.

Intention-to-treat set (ITT population): This set contains all the patients of the enrolment set in whom argatroban was administered. The primary analysis set for the description of the patients, for analyses of efficacy and safety is the ITT population.

Per-protocol set (PP population): The PP population is a subset of the ITT population and includes patients where all inclusion criteria are met, where none of the exclusion criteria applies and where the study was carried out according to the study protocol.

The procedures in case of protocol violations and the assignment of the individual patients to the analysis collectives are determined in consultation with the principal investigator prior to the statistical analysis.

The primary outcome criterion of this study, the mean difference in QTc interval between ECG-2 and ECG-1, is analyzed for the ITT and additionally for the PP sample. Differences in the results between the ITT and PP samples are discussed.

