13.2 Protocol deviations

The classification of protocol deviations into not significant and significant protocol deviations, meaning protocol deviations leading to the exclusion of patients from the PP-set, will be done after data review in co-operation between the sponsor, the principal investigator and [REDACTED]. The decision about the assignment of patients to the analysis sets will be made before data lock. A data review protocol will be prepared.

14 Statistical methodology

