14.3 Confirmatory statistics

Following measurements of QTc will be made for each patient:

- Prior to first bolus dose of argatroban: QTc₁
- Immediately after cardiac intervention in a status of full anticoagulation with argatroban: QTc₂
- > 8 but \leq 28 hours after termination of prolonged argatroban infusion: QTc₃

The statistical hypothesis of this study refers to the difference QTc₂ - QTc₁ = Δ QTc:

H₀: Δ QTc > 10 ms

H_A: Δ QTc \leq 10 ms.

The null hypothesis H₀ states that the mean difference QTc₂ minus QTc₁ is greater 10 ms. The alternative hypothesis H₁ asserts that the mean difference QTc₂ minus QTc₁ is lower or equal 10 ms.

H₀ will be tested by a one-sided one sample t-test with a significance level of alpha=5%. A one-sample t-test can be used to compare a sample mean to a given value. The variable analysed is assumed to be normally distributed.

Data from all patients with measurements QTc₁ and QTc₂ will be included in the analysis of Δ QTc.

Additionally, Δ QTc as well as QTc₁ and QTc₂ will be described by descriptive statistics (mean, standard deviation, median, minimum, maximum, and 95%-confidence

interval). An individual patient listing will be provided with QTc₁, QTc₂, Δ QTc, QTc₃ and the difference QTc₃ minus QTc₁.

The analysis of the primary variable will be based on the ITT sample. It will be repeated for the PP sample. The study report will contain a statement about difference in study results between the ITT and PP sample.

The SAS-statement used to test H₀ is:

```
PROC TTEST DATA=data H0=10 SIDE=L;  
  VAR deltaQTc;  
  RUN;
```

H0=10 requests tests against a null value of 10 ms,

SIDE=L specifies a lower one-sided test, in which the alternative hypothesis indicates a mean less than the null value, and lower one-sided confidence intervals between minus infinity and the upper confidence limit.

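### Does the SAP need a rule for an ITT success that the PP analysis does not confirm, and for treated patients who had no PCI?

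*SAP*

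**What the plan says.** **Deciding set.** Protocol 13.3.5.1 states: "The analysis of the primary variable will be based on the ITT sample". SAP 13.1, 14.3 and 15.5 agree. SAP 13.1 defines ITT by administration of argatroban alone. SAP 14.3 admits to the test every patient who has both QTc1 and QTc2.

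**Role of PP.** SAP 15.5 warns: "It may actually be easier to show non-inferiority in the bigger sample of the ITT population, especially in case of many protocol deviations". It adds: "This underpins the importance of the PP analysis in non-inferiority trials". The primary test is repeated in PP. SAP 14.3 requires: "The study report will contain a statement about difference in study results between the ITT and PP sample". SAP 13.1 says: "Differences in the results between the ITT and PP samples are discussed". PP is the subset that meets the entry criteria and "where the study was carried out according to the study protocol".

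**Patients without PCI.** SAP 15.4 tabulates procedure duration within ITT for patients with and without PCI, and SAP 14.1.9 puts their identification on the data-review agenda. SAP 14.3 defines the second ECG as taken "Immediately after cardiac intervention in a status of full anticoagulation with argatroban".

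**Timing.** SAP 13.2 states: "The decision about the assignment of patients to the analysis sets will be made before data lock".

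**The concern.** The SAP says ITT may make success easier and stresses PP, but attaches no stated conclusion to a PP failure. A reader could fear that the report passes over a discordant PP result.

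Two inputs also look loose. First, the second ECG is tied to the intervention, so it is not explicit which ECG counts when a patient received argatroban but no PCI, or whether that patient belongs in PP. Second, PP is defined in general terms and filled in at a data review from which QTc values are not stated to be withheld. Under Protocol 8.6 the blinded reader's sheets return to the site.

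What would be at stake is the safety conclusion. If some ITT patients carry little argatroban effect at ECG-2, they pull the mean down, and the trial could exclude a 10 ms prolongation too readily.

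**Working it through.** **1. Reproduce the plan's power.** Inputs from Protocol 13.1: one-sided one-sample t-test, alpha 5%, margin 10 ms, n = 45. The SD is not stated. Solving Table 1 for it at true means of 4 to 8 ms gives 9.98 to 10.01, so SD = 10 is used.

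Power = P(T > t(0.95, 44)), where T is non-central t with 44 degrees of freedom and non-centrality (10 − μ)/10 × √45.

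At μ = 3, 4, 5, 6, 7, 8 this gives 0.999, 0.990, 0.951, 0.841, 0.632, 0.373, which matches Table 1.

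**2. Effect of sample size alone.** The observed mean must fall below 10 − t(0.95, n−1) × 10/√n:
- n = 45: 10 − 1.680 × 10/√45 = 7.50 ms
- n = 40: 10 − 1.685 × 10/√40 = 7.34 ms
- n = 36: 10 − 1.690 × 10/√36 = 7.18 ms

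A PP set with the same mean can therefore fail merely because it is smaller.

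**3. Size of the feared bias.** Assume a true mean of 10 ms in most patients and a lower effect in k of 45, and let PP drop exactly those k. For k = 5 and zero effect, the ITT mean is 40 × 10/45 = 8.89 ms. Each cell below, from simulation with SD 10, shows the probability that ITT succeeds and, in brackets, the share of those successes that PP does not confirm.

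| k of 45 | Same effect (10 ms) | Half effect (5 ms) | Zero effect |
|---|---|---|---|
| 2 | 0.050 (18%) | 0.066 (29%) | 0.083 (41%) |
| 4 | 0.050 (25%) | 0.086 (46%) | 0.131 (62%) |
| 5 | 0.050 (28%) | 0.096 (52%) | 0.160 (69%) |
| 9 | 0.050 (38%) | 0.154 (69%) | 0.325 (85%) |

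The PP test itself stays at 0.05 throughout. With 80% of the effect (8 ms), ITT succeeds in 0.056, 0.063 and 0.067 for k = 2, 4, 5.

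**4. What a scripted conclusion would change.** ITT would still decide, so the first figure in every cell is unchanged. The bracketed share comes from running PP beside ITT and reporting the difference, which SAP 14.3 already requires. The first column is the background: with no bias at all, discordance is common. At a true mean of 6 ms in everyone, ITT succeeds and PP fails in 0.030, 0.060 and 0.101 of trials when 2, 5 or 9 patients leave PP.

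**5. Do patients without PCI count?** Set the definitions side by side:
- ITT requires argatroban, not PCI (SAP 13.1).
- Both ECGs present means inclusion in the test (SAP 14.3).
- Protocol 6.3 takes the procedure from placement to removal of the vascular sheath, and SAP 15.4 expects a duration for patients without PCI. A procedure end at which ECG-2 can be recorded is therefore foreseen for them.

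The natural reading is that such a patient counts.

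**The case for a change.** The strongest case for a change is that the SAP raises the ITT problem itself and then stops short. Patients without PCI are plainly expected, yet their PP status and the result of identifying them are not written down. The trial is open, the internal data monitors see ECG data at once (Protocol 1.2), and the sponsor and principal investigator classify the deviations. Before data lock is not the same as blind to QTc. There is also a route to lower exposure: the infusion stops at the end of the procedure, ECG-2 follows with no limit in minutes, the effect was seen to wear off within 30 minutes (Protocol 6.3), and no ACT is required at ECG-2.

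These observations are correct, but they carry less weight than they seem to:
- Classification of deviations governs PP, which does not decide. Leaving a treated patient with both ECGs out of the ITT test would depart visibly from SAP 13.1 and 14.3.
- No document says that patients without PCI are under-exposed. They too receive a bolus and infusion with an ACT check.
- A fixed list of exposure deviations is harder to write than it looks. The last recorded ACT is the follow-up value, which Protocol 6.3 and 10.4 intend to be at most 160 s, so comparing it with the 300 s target would empty PP. A patient still below target after the prescribed adjustment has followed the protocol.
- Late text would bring little extra blinding. The SAP cites a data management plan dated 15 April 2021, after the planned last visit in Q1 2021, and Protocol 6.2 expects ECG readings within 48 hours.

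**Conclusion.** No change to the plan is needed. The deciding set is stated, inclusion in the test follows from the definitions, and an ITT/PP difference must be reported and discussed. What is missing is narrow: the wording of that statement, an explicit line that ECG-2 at the end of the procedure serves as QTc2 when no PCI was done, and the PP status of those patients. A competent analyst would show the mean and upper one-sided 95% limit for both sets and say whether a discordance reflects a higher PP mean or only fewer patients. The data review before lock already has the no-PCI patients and the set assignment on its agenda.

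The inflation from 0.05 to between 0.083 and 0.325 depends on SD 10, a true mean of exactly 10 ms and zero effect in 2 to 9 of 45 patients. At 80% of the effect it is at most 0.067 for up to 5 patients, and with full effect there is none. Scripting the PP sentence would remove none of it. Confidence is moderate, because the documents give neither the number of treated patients without PCI nor their exposure at ECG-2.

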15.5.2 Laboratory results

Hematocrit at screening, during treatment and at follow-up; classification of hematocrit values to reference range values (see DMP).

A listing of each abnormal laboratory value will be provided.

15.6 Analysis of safety

Evaluation of safety will be performed for the ITT analysis set. If present, adverse events in patients who are not included in the ITT population will be described separately.

15.6.1 Adverse events

Adverse events (AE) data will be processed in the statistical analyses after coding according to the MedDRA dictionary. In an individual patient data listing verbatim adverse events term will be depicted along with the assigned MedDRA preferred term. Statistical analysis will not take in account MedDRA low level terms but will start at preferred term level.

In addition to an analysis of all adverse events, adverse events with a causal relation to the treatment, that is adverse reactions, will be analyzed separately.

The incidence of haemorrhagic events according to the definition of CABG-related bleeding will be presented.

15.6.2 Individual patient data listing of adverse events

All adverse events, treatment emergent or not, will be listed in an individual patient data listing. Verbatim adverse event terms will be depicted along with the assigned

MedDRA preferred term, treatment, intensity, seriousness, relation, measures regarding study treatment and patient, start of AE, end of AE, and visit dates.

A separate listing will be provided for deaths, other serious adverse events, and other significant adverse events.

16 Statistical software used for analysis

Statistical analysis will be conducted using the program system SAS (Version 9.4 or later) under the Microsoft Windows 10 Professional operating system (or later) at the computer facilities of [REDACTED].

17 Reporting of analyses

Percentage values will be printed with two digits to the right of the decimal point. All p-values will be given by four digits to the right of the decimal point.

Verbatim terms documented on the CRF will be presented as entered.

The statistical analysis output will be prepared in English. The separate individual patient data listings will be in original CRF language. The separate individual patient data listing will include patients excluded from the ITT analysis set, if any.

18 Changes to planned analyses

This statistical analysis plan does currently not include any relevant changes to the planned analyses that are described in the study protocol.

[figure not shown]
Any changes made to the SAP after sign-off must be signed-off as a SAP Amendment, detailing the old text, revised text and reason for change.

19 Graphics, analysis tables and listings

19.1 Graphics

[figure not shown]
19.1.1 Pie charts

Pie charts will be used to illustrate numerical proportion.

[figure not shown]

19.1.2 Plots of means and box plots

Mean plots may be used to see if means varies between different groups of patients or how means are changing over time.

[figure not shown]

Box plots may be used to detect and illustrate location (mean, median) and variation changes between different groups of patients or between different points in time.

[figure not shown]

19.1.3 Histograms

To graphically summarize the distribution of univariate data histograms will be used where appropriate.

Histograms will also be used to show relative frequencies in case of multiple response variables like concomitant diseases.

Histograms may also be used to compare numerical proportions.
